Visit Number/Description	Screening	Baseline	Week 1, Day 1	Week 1, Day 2	Week 1, Day 4	Week 1, Day 6	Week 1, Day 7	Week 2, Day 8 & 9	Week 2, Day 10	Week 2, Day 14	Week 3	Week 4	Week 5	Week 6	Week 7	Week 9	Week 11	Week 13	Week 18	Week 35	Week 47	Week 52			
Visit Day	-90 to -30	-48 to -16	1	2	4	6	7	8 & 9	10	14	21	28	34	42	48	60	74	90	120	240	328	360	360	360	
Visit Window (± days)			0	0	0	0	0	0	0	1	1	1	1	3	3	3	3	7	7	14	7	7	7	7	
International normalized ratio (INR), Hepatitis A virus (anti-HAV) immunoglobulin M Hepatitis B surface antigen, Hepatitis C antibody ^l	X																							X	
Biomarker (creatinine kinase) ^l		X			X						X	X	X	X		X	X	X	X	X	X			X	X
Banked biospecimens for biomarkers ^m	X																							X	
Banked biospecimens for genetics ⁿ																								X	
Urine Samples																									
Clinical safety (urinalysis) ^l	X		X	X	X						X			X			X			X			X	X ^g	
Banked biospecimens for biomarkers ^m	X																							X	

PFIZER CONFIDENTIAL

CT02-GSOP Clinical Protocol Template Phase 1 2 3 4 (04 September 2018)

Page 190

Period	Screening	Baseline	Main Study Period (Year 1)																					Early Discontinuation Visit ^a	
			Visit 1 ^a	Visit 2 ^c	Visit 3 ^d	Visit 4	Visit 5	Visit 6	Visit 7	Visit 8 & 9	Visit 10	Visit 11	Visit 12 ^e	Visit 12.2	Visit 13	Visit 13.1 ^{kk}	Visit 13.2 ^e	Visit 14 ^b	Visit 14.2 ^e	Visit 15 ^e	Visit 16	Visit 17	Visit 18 ^f		
Visit Number/ Description	Visit 1 ^a	Visit 2 ^c	Visit 3 ^d	Visit 4	Visit 5	Visit 6	Visit 7	Visit 8 & 9	Visit 10	Visit 11	Visit 12 ^e	Visit 12.2	Visit 13	Visit 13.1 ^{kk}	Visit 13.2 ^e	Visit 14 ^b	Visit 14.2 ^e	Visit 15 ^e	Visit 16	Visit 17	Visit 18 ^f	Visit 19 ^b	Wee k 52		
	Screening	Baseline	Wee k 1, Day 1	Wee k 1, Day 2	Wee k 1, Day 4	Wee k 1, Day 6	Wee k 1, Day 7	Wee k 1, Day 8 & 9	Wee k 2, Day 10	Wee k 2, Day 14	Wee k 2, Day 14	Wee k 3	Wee k 4	Week 5	Week 6	Week 7	Wee k 9	Wee k 11	Wee k 13	Wee k 18	Wee k 35	Wee k 47			
Visit Day	-90 to -30	-48 to -16	1	2	4	6	7	8 & 9	10	14	21	28	34	42	48	60	74	90	120	240	328	360	360		
Visit Window (± days)			0	0	0	0	0	0	0	1	1	1	1	3	3	3	3	3	7	7	14	7	7		
Viral Vector Shedding ^z	X		X	X	X		X		X	X	X		X			X		X	X	X		X	X ^g		
Saliva Samples																									
Viral Vector Shedding ^z	X		X	X	X		X		X	X	X		X			X		X	X	X		X	X ^g		
Tissue Samples																									
Muscle biopsy ^o		X																						X ^x	
Imaging Assessments																									
Echocardiogram ^p	X																							X	X ^g

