- NAb to AAV9, ADA to mini-dystrophin and AAV9, ELISpot to mini-dystrophin and AAV9: Only if the participant discontinues the study before Visit 37 (Year 3, Day 1110).
- Clinical safety: Only if the previous analysis had been done more than 1 month before the date of the Early Discontinuation visit.
- Echocardiogram: Only if the previous echocardiogram had been done more than 6 months before the date of the Early Discontinuation Visit.
- FVC: Only if the previous FVC had been assessed more than 2 months before the date of the Early Discontinuation Visit.
- Viral vector shedding: For any given matrix, if the sample(s) had still been collected at the participant's last study visit, it should also be collected at the Early Discontinuation Visit.

h. **Brief physical and neurological examinations**, as described in [Section 8.2](#), are acceptable post-baseline unless safety concerns warrant full examination.

i. **O2 saturation** will only be measured before the start of the IP infusion and during the inpatient stay post IP administration.

j. **Vital signs** will be measured 3 times per day during the inpatient stay post IP administration.

Period	Screening	Baseline	Main Study Period (Year 1)																					Early Discontinuation Visit ^g
			Visit 1 ^a	Visit 2 ^c	Visit 3 ^d	Visit 4	Visit 5	Visit 6	Visit 7	Visit 8 & 9	Visit 10	Visit 11	Visit 12 ^e	Visit 12.2	Visit 13	Visit 13.1 ^{kk}	Visit 13.2 ^e	Visit 14 ^b	Visit 14.2 ^e	Visit 15 ^e	Visit 16	Visit 17	Visit 18 ^f	
Visit Number/ Description	Visit 1 ^a	Visit 2 ^c	Week 1, Day 1	Week 1, Day 2	Week 1, Day 4	Week 1, Day 6	Week 1, Day 7	Week 2, Day 8 & 9	Week 2, Day 10	Week 2, Day 14	Week 3	Week 4	Week 5	Week 6	Week 7	Week 9	Week 11	Week 13	Week 18	Week 35	Week 47	Week 52		
	Screening	Baseline																						
Visit Day	-90 to -30	-48 to -16	1	2	4	6	7	8 & 9	10	14	21	28	34	42	48	60	74	90	120	240	328	360		
Visit Window (± days)			0	0	0	0	0	0	0	1	1	1	1	3	3	3	3	7	7	14	7			

k. **12-Lead ECG** will be collected and read locally for immediate interpretation and safety monitoring and will be submitted to a central laboratory for standardized interpretation.

- l. **Clinical laboratory tests** are described in detail in [Table 3 \(Appendix 2\)](#).
 - For urinalysis, a microscopic analysis will be performed only if urine dipstick is positive for blood, protein, nitrites or leukocyte esterase.

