- gg. The Investigator will discuss with the participant and caregiver the importance of having a baseline cardiac MRI, even under general anesthesia to be able to assess and manage potential cardiac adverse events during the study. This discussion and the decision to perform or not a baseline cardiac MRI will be documented in the participant's records. A Participant requiring anesthesia or unable to undergo investigation with closed MRI (eg, metal implants) may be exempt, and will be allowed to be randomized in the study without a cardiac MRI. Sites will be responsible for confirming participant eligibility to undergo MRI scanning and gadolinium contrast administration ([Section 2.3.3.7](#)). If the site considers gadolinium contrast administration unsafe, or if the participant has a history of allergy to gadolinium, cardiac MRI without contrast administration will be performed. It is important that the investigator discusses with the participant and/or caregivers that a cardiac MRI even under general anesthesia may be required in certain situations ([Section 8.2.8](#)).
- hh. Cardiac MRI may be performed at any time between the first day of the Screening Visit (Visit 1) and the Day 1 Visit (Visit 3), and after randomization, as long as it is done before Day 1 (Visit 3). If a prior cardiac MRI was performed within 6 months of the Screening Visit (with gadolinium, or without gadolinium if contrast administration is contraindicated), and results are available, then a cardiac MRI at screening will not be performed. Only participants with a pre-IP administration cardiac MRI will have a follow-up cardiac MRI on Day 360 (Visit 19) and on Day 749 (Visit 35).
- ii. Participants will be assessed by a cardiologist at the Screening Visit, see [Section 5.2](#), exclusion criteria 16 and 17.

Period	Screening	Baseline	Main Study Period (Year 1)																					Early Discontinuation Visit ^{aa}
			Visit 1 ^a	Visit 2 ^c	Visit 3 ^d	Visit 4	Visit 5	Visit 6	Visit 7	Visit 8 & 9	Visit 10	Visit 11	Visit 12 ^e	Visit 12.2	Visit 13	Visit 13.1 ^{kk}	Visit 13.2 ^e	Visit 14 ^b	Visit 14.2 ^e	Visit 15 ^e	Visit 16	Visit 17	Visit 18 ^f	
Visit Number/ Description	Visit 1 ^a	Visit 2 ^c	Week 1, Day 1	Week 1, Day 2	Week 1, Day 4	Week 1, Day 6	Week 1, Day 7	Week 2, Day 8 & 9	Week 2, Day 10	Week 2, Day 14	Week 3	Week 4	Week 5	Week 6	Week 7	Week 9	Week 11	Week 13	Week 18	Week 35	Week 47	Week 52	Week 52	
	Screening	Baseline																						

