14. LVEF <50% on echocardiogram performed at the Screening Visit (Visit 1), as evaluated by the central reader.
15. Participants with the following genetic abnormalities in the dystrophin gene as confirmed by the investigator based on the review of DMD genetic testing:
 - a. Any mutation (exon deletion, exon duplication, insertion, or point mutation) affecting any exon between exon 9 and exon 13, inclusive; OR
 - b. A deletion that affects both exon 29 and exon 30;OR
 - c. A deletion that affects any exons between 56-71, inclusive.

For details on the retrospective assessment of exclusion criterion 15, please see [Appendix 12](#).

16. Cardiac pathologies, as evaluated by a pediatric cardiologist at the Screening Visit (Visit 1):
 - a. Diagnosis of myocarditis (eg, viral): either based on prior medical history or based on findings in cardiac imaging tests;
 - b. Any other cardiac history, and/or condition and/or abnormalities in cardiac imaging, that determine that the participant should not be included in the study, as per the cardiologist.
17. Not a candidate for mechanical cardiac or respiratory support, or any other invasive intervention, if indicated for management of an acute event as determined by the cardiologist in consultation with the investigator at the Screening Visit (Visit 1).

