		
In Section 7.1, added ineligibility criterion for LVEF <50% on echocardiogram performed at Day 360 (Visit 19), or at the unplanned visit to re-assess eligibility for Year 2 IP administration, as evaluated by the central reader. This applies only for participants in Cohort 2, confirmed by the unblinded medical monitor.
 
Rationale: To ensure that participants in Cohort 2 who experience a clinically relevant decrease in LVEF that could increase the risk of cardiac complications after treatment with fordadistrogene movaparvovec, do not receive IP (fordadistrogene movaparvovec) in Year 2.

		
In Section 7.1, added ineligibility criterion for diagnosis of myocarditis. This applies only for participants in Cohort 2, confirmed by the unblinded medical monitor.
 
Rationale: To ensure that participants in Cohort 2 with a diagnosis of myocarditis that could increase the risk of cardiac complications after treatment with fordadistrogene movaparvovec, do not receive IP (fordadistrogene movaparvovec) in Year 2.

		
In Section 7.1, added ineligibility criterion for a participant who is not a candidate for mechanical cardiac or respiratory support, or any other invasive intervention, if indicated for

Document History		
Document	Version Date	Summary of Changes and Rationale

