		
management of an acute event as determined by the cardiologist in consultation with the investigator. This applies only for participants in Cohort 2, confirmed by the unblinded medical monitor.
 
Rationale: To ensure that participants who are not candidates for invasive measures that may be required for the treatment of some SAEs, for example cardiac SAEs, do not receive IP (fordadistrogene movaparvovec) in Year 2 as they would be considered too fragile to be suitable for these potentially required measures.
 
In Section 8.2.7. Figure 3. Management of Elevated Cardiac Troponin I (cTn-I), added new instructions for the management of participants with elevated levels of cardiac troponin I or T, including requirement for echocardiographic assessments, assessment of NT-ProBNP/BNP, and instructions on when to admit participants with elevated cardiac troponin to the hospital, even if asymptomatic. Updated the time to repeat an elevated cTn-I/ cTn-T from “72-96 hours” to “approximately 48 to 96 hours”.
 
Rationale: To improve the ability of the sites and the study team to promptly ascertain if an elevated cardiac troponin reflects an acute cardiac event or if it is related to the fluctuations usually seen in patients with DMD, to allow for prompt management if necessary.
 
In Section 8.2.10, added a reminder for the investigators to discuss with participants and caregivers the potential need for participants with immune-mediated events to be admitted to the intensive care or coronary unit, and to require invasive measures such as the placement of a central catheter, performance of an

Document History		
Document	Version Date	Summary of Changes and Rationale

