		
endomyocardial biopsy, and use of mechanic respiratory or circulatory support.
 
Rationale: To make participants and caregivers aware of the management strategies that may be required in cases of immune-mediated complications, including cardiac events.
 
In Section 1.3.1, removed footnote “e”, and in Section 1.3.2, removed footnote “b” due to addition of inpatient hospital stay for at least 7 days post IP administration.
 
Other changes:
 
In Sections 1.3.1, footnotes “b” and “f”, 1.3.2, footnotes “bb” and “cc”, 5.2, 6.5.1, 6.5.2, 7.1, and 8.2.10, provided instructions for the management of Cohort 1 and Cohort 2 participants retrospectively confirmed to meet exclusion criterion 15 after the enrollment and dosing pause implemented on 04 August 2021.
 
Rationale: To ensure that participants in Cohort 1 who had already received fordadistrogene movaparvovec and were retrospectively found to meet exclusion criterion 15 remain in the study for safety monitoring, but do not receive placebo in Year 2, given that it also requires a regimen of high doses of steroids for 3 months and very frequent visits to the site with associated laboratory tests.
 
Rationale: To also ensure that participants in Cohort 2 who received placebo in Year 1 and would receive fordadistrogene movaparvovec in Year 2 are withdrawn from the study to allow them to pursue other treatment(s).

Document History		
Document	Version Date	Summary of Changes and Rationale

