		
mini-dystrophin will be reviewed by the unblinded medical monitor on an ongoing basis.
 
As recommended by the E-DMC to optimize safety monitoring.
 
In Sections 1.3.1, 1.3.2, and 10.9.1, added cardiac troponin I assessments to Days 28, 48, 74, and 90 in Year 1 and Days 417, 437, 463, and 479 in Year 2 in the Schedule of Activities. Removed cardiac troponin I assessments on Day 7 in Years 1 and 2 in the Schedule of Activities due to addition of central laboratory assessments on these days in Section 10.2 (Appendix 2).
 
To optimize the monitoring for myocardial injury during the period when the risk of cellular immune response is anticipated to be most likely.
 
In Sections 1.3.1, 1.3.2, 3.2, and 10.9.1, added cardiac MRI assessments to Screening Visit (Visit 1) or Baseline (Visit 2) and Week 52 in Years 1 and 2, relevant footnotes to Schedule of Activities, and associated objectives and endpoints.
 
To establish presence or absence of cardiac injury prior to delivery of gene therapy, and to aid in interpretation of cardiac MRI that may be performed in response to adverse events.
 
In Sections 1.3.1, 1.3.2, 5.3, 5.6, 7.1, and 10.9.1, clarified that participants who exceed the time between the Screening Visit (Visit 1) and the Day 1 Visit (Visit 3), or the time between Day 360 Visit (Visit 19) and the planned Day 390 Visit (Visit 20) due to operational or administrative reasons (eg, enrollment pause due to regulatory or safety review, operational issues causing significant delays) will not be screen failed/withdrawn from the study, but will repeat some tests and assessments to

Document History		
Document	Version Date	Summary of Changes and Rationale

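### A pre-dose echocardiogram can cancel the Early Discontinuation echocardiogram for about 3 to 5 months after dosing, so an early leaver may contribute no post-dose LVEF

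*Protocol*

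**What the plan says.** Footnote g of the Year 1 schedule in Section 10.10.1.1 limits the exit scan as follows: "Echocardiogram: Only if the previous echocardiogram had been done more than 6 months before the date of the Early Discontinuation Visit". The same line stands in the Year 1 schedules for Germany, Russia and Israel (Sections 10.14.1, 10.15.1 and 10.16.1). It also stands in footnote e of every Year 2 schedule shown. No version mentions dosing.

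The echocardiogram row of the Year 1 schedule is marked at Screening, at Day 360 and, conditionally, at the Early Discontinuation Visit. The Year 2 schedules mark Day 749 and then the annual follow-up visits. Nothing is scheduled between Screening and Day 360, or between Day 360 and Day 749. Dosing falls on Day 1 and Day 390, inside those two gaps.

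The Screening scan serves eligibility: Section 10.14.4 excludes "LVEF <50% on echocardiogram performed at the Screening Visit (Visit 1), as evaluated by the central reader". Cardiac MRI does not fill the gap. Footnote hh of Section 10.10.1.1 says "Only participants with a pre-IP administration cardiac MRI will have a follow-up cardiac MRI on Day 360" and on Day 749, and the schedules mark no MRI at the exit visit.

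The protocol does concentrate cardiac monitoring in the first months after dosing. The Amendment 6 entry in Appendix 17 explains the troponin tests added at Days 28, 48, 74 and 90, and at Days 417, 437, 463 and 479, by this aim: "To optimize the monitoring for myocardial injury during the period when the risk of cellular immune response is anticipated to be most likely".

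**The concern.** A recency limit on an exit assessment makes sense when the previous result still describes the participant. For most items in the footnote that is plausible. Clinical safety tests, for example, have a 1-month limit and are repeated often after dosing, so their previous value is usually a post-dose one. The echocardiogram has the longest limit in the footnote, 6 months, and no scheduled measurement in the year that follows each infusion. For an early leaver the previous scan is therefore normally the one taken before the infusion. It may be recent by the calendar, yet it says nothing about the effect of the product.

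At stake is LVEF after exposure in participants who leave while troponin is being followed most closely. Appendix 17 (Amendment 6) also records that cardiac injury has been seen in clinical studies of this product. A scan not done at the exit visit cannot be recovered later.

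**Working it through.** The protocol gives no derived figure to reproduce, so this is date arithmetic on its own schedule. It does not define 6 months in days; I assume 180 to 184.

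**Inputs.** Screening is on Day -90 to -30, Year 1 dosing on Day 1, Visit 19 on Day 360 (±7) and Visit 20 dosing on Day 390 (±3), all from the schedules of activities.

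**Formula.** Last day on which the exit scan is waived = day of previous scan + 6 months. If the calendar has no Day 0, the Year 1 results move one day later.

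**Year 1**

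| Screening scan | + 180 days | + 184 days | Range, with or without a Day 0 |
|---|---|---|---|
| Day -90 | Day 90 | Day 94 | Day 90-95 |
| Day -60 | Day 120 | Day 124 | Day 120-125 |
| Day -30 | Day 150 | Day 154 | Day 150-155 |

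The waiver therefore lasts about 3 months after dosing for the earliest permitted Screening day and about 5 months for the latest.

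**Year 2, undelayed dosing**

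- Last waived day: 360 + 180 = Day 540, to 360 + 184 = Day 544.
- Days after infusion: 540 - 390 = 150, to 544 - 390 = 154.
- Extremes of the visit windows: 353 + 180 - 393 = 140 days, and 367 + 184 - 387 = 164 days.

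This matters for those described in Appendix 17 as "participants in Cohort 2 who received placebo in Year 1 and would receive fordadistrogene movaparvovec in Year 2". Cohort 1 had gene therapy in Year 1, so its Day 360 scan is already a post-treatment one.

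**Against the added troponin tests.** The Year 1 tests at Days 28, 48, 74 and 90 all fall on or before the earliest end of the waiver, Day 90. The Year 2 tests at Days 417 to 479 lie 27 to 89 days after dosing (417 - 390 and 479 - 390), well inside the 140 to 164 days of waiver. A leaver at any of these nominal test days would have the exit scan cancelled by the pre-dose one, provided dosing was on schedule and no scan was done in between.

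**Delays.** If Screening to dosing runs past 90 days, some assessments are repeated under Sections 5.3 and 5.6, which are not in the part shown. A scan repeated close to dosing would lengthen the post-dose waiver, and an old unrepeated one would shorten it. If Year 2 dosing slips more than 6 months beyond Day 360 with no repeat scan, the waiver has lapsed before the infusion.

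**The case against.** The strongest reply is that this is a consistent design. No continuing participant has a scheduled echocardiogram in the months after dosing either. Monitoring relies on troponin and clinical triggers, and those who do badly are the most likely to be scanned outside the schedule. Appendix 17 (Amendment 8) describes Section 8.2.7 as covering "management of participants with elevated levels of cardiac troponin I or T, including requirement for echocardiographic assessments". Troponin, ECG and physical examination remain at the exit visit without the 6-month condition. All of this stands, and it confines the loss mainly to an LVEF value in leavers without a cardiac trigger. It does not remove the point. A continuing participant reaches the next scheduled scan, whereas for a leaver the exit visit is the last opportunity.

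Four stronger readings are tempting and are not supported:

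- **That early leavers exit without cardiac assessment.** The retained tests contradict this.
- **That every Year 2 participant is affected.** Only Cohort 2 receives gene therapy then, and dosing pauses move the dates.
- **That the protocol defines Days 28 to 90 as the cardiac risk period.** The amendment entry gives a reason for adding particular troponin tests and sets no window.
- **That cardiac safety summaries are biased towards completers.** The pages shown give neither the number leaving in these months nor the LVEF summary concerned.

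Sections 8.2.6 to 8.2.8 are not in the part shown and could add a requirement for a scan.

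**Conclusion.** The point holds as a gap in data collection. It is not an arithmetic error, and it does not show that safety monitoring is absent. As the footnotes stand, a participant who leaves within about 3 to 5 months of Year 1 dosing can exit with no scheduled post-dose echocardiogram. The same holds for a Cohort 2 participant who leaves within about 5 months of an undelayed Year 2 dosing. In both cases the exception is a scan triggered by elevated troponin or another event. In Year 1 the waiver applies to both arms, so a control value can be lost as well as a treated one.

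The durations rest on 6 months being 180 to 184 days, on dosing at the scheduled time, and on nothing in the sections not shown overriding the footnote. The number of participants concerned is probably small, and any effect on the cardiac safety results is unquantified. The change is still worth making because the lost value is irrecoverable and the remedy is small.

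**What to change.** Reconcile the 6-month waiver in Year 1 footnote g and Year 2 footnote e, in every schedule, with the protocol's post-dose cardiac monitoring. The aim is that a scan taken before the most recent infusion does not by itself count as the recent one that cancels the exit scan. The sponsor's clinical team should set the exact condition and check it against Sections 8.2.6 to 8.2.8. It should apply identically to both cohorts so that the presence or absence of an exit scan does not reveal assignment.

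The cost is one sentence per footnote and one non-invasive scan, already listed for this visit, in the few participants who leave early.

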10.10.1.2. Schedule of Activities – Year 2 and Long Term Follow Up

Period	Year 2																				Long-term follow up		Early Discontinuation Visit ^e	
	Visit 20 ^{a,bb,cc}	Visit 21 ^{bb,cc}	Visit 22 ^{bb,cc}	Visit 23 ^{bb,cc}	Visit 24 ^{bb,cc}	Visit 25 ^{bb,cc & 26^{bb,cc}}	Visit 27 ^{bb,cc}	Visit 28 ^{bb,cc}	Visit 29 ^{bb,cc}	Visit 29.2 ^{b,bb,cc}	Visit 30 ^{bb,cc}	Visit 30.1 ^{ee,bb,cc}	Visit 30.2 ^{b,bb,cc}	Visit 31 ^{e,cc}	Visit 31.2 ^{b,cc}	Visit 32 ^{b,cc}	Visit 33	Visit 34	Visit 35	Visits 36, 38, 40, 42 ^d	Visits 37, 39, 41, 43 ^d			
Visit Number/Description	Year 2, Week 1, Day 1	Year 2, Week 1, Day 2	Year 2, Week 1, Day 4	Year 2, Week 1, Day 6	Year 2, Week 1, Day 7	Year 2, Week 2, Days 8 & 9	Year 2, Week 2, Day 10	Year 2, Week 2, Day 14	Year 2, Week 3	Year 2, Week 4	Year 2, Week 5	Year 2, Week 6	Year 2, Week 7	Year 2, Week 9	Year 2, Week 11	Year 2, Week 13	Year 2, Week 18	Year 2, Week 35	Year 2, Week 52	Years 3, 4, 5, 6 ^d	Years 3, 4, 5, 6 ^d	Early Discontinuation Visit ^e		
Visit Day	390	391	393	395	396	397& 398	399	403	410	417	423	431	437	449	463	479	509	629	749	930, 1290, 1650, 2010 ^d	1110, 1470, 1830, 2190 ^d	Visit ^e		
Visit Window (\pm days)	3 ^f	2 ^f	2 ^f	2 ^f	2 ^f	2 ^f	2 ^f	3 ^f	3 ^f	3 ^f	3 ^f	3 ^f	3 ^f	3 ^f	3 ^f	3 ^f	7 ^f	7 ^f	7 ^f	30 ^f	30 ^f	Visit ^e		
Eligibility for Year 2 IP administration ^f	X																						Visit ^e	
Hospital stay ^{dd}	X	→	→	→	→	X																	Visit ^e	
Physical examination ^g	X	X	X		X		X	X			X			X				X	X	X	X	X	Visit ^e	
Neurological examination ^g			X		X		X	X			X			X				X	X	X	X	X	Visit ^e	
Height and Weight												X						X	X	X	X	X	Visit ^e	
Vital signs (supine BP, respiration, PR, body temp, and O ₂ saturation) ^{h,i}	X	X	X		X		X	X			X			X			X	X	X	X	X	Visit ^e		
12-Lead ECG ^j	X				X			X												X		X	Visit ^e	
CBCL																				X	X	X	Visit ^e	
Laboratory Assessments ^k																							Visit ^e	
Blood Samples																								Visit ^e
NAb to AAV9														X							X		X	Visit ^e
ADA to mini-dystrophin and AAV9										X ^z	X ^z	X ^z	X					X		X		X	Visit ^e	
ELISpot to mini-dystrophin and AAV9	X																X					X ^w	Visit ^e	
Viral Vector Shedding ^u								X						X			X	X	X			X	Visit ^e	

PFIZER CONFIDENTIAL

CT02-GSOP Clinical Protocol Template Phase 1 2 3 4 (04 September 2018)

Period	Year 2																				Long-term follow up		Early Discontinuation Visit ^e
	Visit 20 ^{a,bb,cc}	Visit 21 ^{bb,cc}	Visit 22 ^{bb,cc}	Visit 23 ^{bb,cc}	Visit 24 ^{bb,cc}	Visit 25 ^{bb,cc} & 26 ^{bb,cc}	Visit 27 ^{bb,cc}	Visit 28 ^{bb,cc}	Visit 29 ^{bb,cc}	Visit 29.2 ^{bb,cc}	Visit 30 ^{bb,cc}	Visit 30.1 ^{bb,cc}	Visit 30.2 ^{bb,cc}	Visit 31 ^{cc}	Visit 31.2 ^{bb,cc}	Visit 32 ^{bb,cc}	Visit 33	Visit 34	Visit 35	Visits 36, 38, 40, 42 ^d	Visits 37, 39, 41, 43 ^d		
Visit Number/Description	Year 2, Week 1, Day 1	Year 2, Week 1, Day 2	Year 2, Week 1, Day 4	Year 2, Week 1, Day 6	Year 2, Week 1, Day 7	Year 2, Week 2, Days 8 &9	Year 2, Week 2, Day 10	Year 2, Week 2, Day 14	Year 2, Week 3	Year 2, Week 4	Year 2, Week 5	Year 2, Week 6	Year 2, Week 7	Year 2, Week 9	Year 2, Week 11	Year 2, Week 13	Year 2, Week 18	Year 2, Week 35	Year 2, Week 52	Years 3, 4, 5, 6 ^d	Years 3, 4, 5, 6 ^d		
Visit Day	390	391	393	395	396	397& 398	399	403	410	417	423	431	437	449	463	479	509	629	749	930, 1290, 1650, 2010 ^d	1110, 1470, 1830, 2190 ^d		
Visit Window (\pm days)	3 ^f	2 ^f	2 ^f	2 ^f	2 ^f	2 ^f	2 ^f	3 ^f	3 ^f	3 ^f	3 ^f	3 ^f	3 ^f	3 ^{f,c}	3 ^f	3 ^f	7 ^f	7 ^f	7 ^f	30 ^f	30 ^f		
Clinical safety (hematology, other) ^k		X	X					X	X		X			X			X	X	X	X	X	X	X ^e
Chemistry and hepatic safety ^k		X	X					X	X	X ^y	X		X	X	X	X	X	X	X	X	X	X	
Post IP intensified safety monitoring ^{k,s}		X	X					X	X		X												
Local and central laboratory testing ^x	X	X	X	X	X	X	X																
Cardiac Troponin I-central laboratory										X	X	X	X	X	X	X	X	X	X	X	X	X	
Cardiac troponin I or T-local laboratory	X ^{ff}	X	X	X		X ^{gg}	X																
Biomarker (creatinine kinase) ^k			X					X	X	X	X		X	X	X	X	X	X	X	X	X	X	
Banked biospecimens for biomarkers ^l																			X	X			
Urine Samples																							
Clinical safety (urinalysis) ^k	X	X	X					X	X		X		X		X		X	X	X	X	X	X	X ^e
Banked biospecimens for biomarkers ^l																			X	X			
Viral Vector Shedding ^u					X				X					X		X	X	X	X	X	X	X	X ^e

PFIZER CONFIDENTIAL

CT02-GSOP Clinical Protocol Template Phase 1 2 3 4 (04 September 2018)

Page 203

Period	Year 2																				Long-term follow up		Early Discontinuation Visit ^e	
	Visit 20 ^{a,bb,cc}	Visit 21 ^{bb,cc}	Visit 22 ^{bb,cc}	Visit 23 ^{bb,cc}	Visit 24 ^{bb,cc}	Visit 25 ^{bb,cc & 26^{bb,cc}}	Visit 27 ^{bb,cc}	Visit 28 ^{bb,cc}	Visit 29 ^{bb,cc}	Visit 29.2 ^{b,cc}	Visit 30 ^{bb,cc}	Visit 30.1 ^{ee,bb,cc}	Visit 30.2 ^{b,cc}	Visit 31 ^{c,cc}	Visit 31.2 ^{b,cc}	Visit 32 ^{b,cc}	Visit 33	Visit 34	Visit 35	Visits 36,	Visits 37, 39,			
Visit Number/Description	Year 2, Week 1, Day 1	Year 2, Week 1, Day 1	Year 2, Week 1, Day 1	Year 2, Week 1, Day 1	Year 2, Week 2, Days 8 &9	Year 2, Week 2, Day 10	Year 2, Week 2, Day 14	Year 2, Week 3	Year 2, Week 4	Year 2, Week 5	Year 2, Week 6	Year 2, Week 7	Year 2, Week 9	Year 2, Week 11	Year 2, Week 13	Year 2, Week 18	Year 2, Week 35	Year 2, Week 52	Years 3, 4, 5, 6 ^d	Years 3, 4, 5, 6 ^d				
Visit Day	390	391	393	395	396	397& 398	399	403	410	417	423	431	437	449	463	479	509	629	749	930, 1290, 1650, 2010 ^d	1110, 1470, 1830, 2190 ^d			
Visit Window (\pm days)	3 ^f	2 ^f	2 ^f	2 ^f	2 ^f	2 ^f	2 ^f	3 ^f	3 ^f	3 ^f	3 ^f	3 ^f	3 ^f	3 ^{f,c}	3 ^f	3 ^f	7 ^f	7 ^f	7 ^f	30 ^f	30 ^f			
Saliva Samples																								
Viral Vector Shedding ^u					X				X					X		X	X	X	X		X	X ^e		
Tissue Sample																								
Muscle Biopsy																							X ^{hh}	
Imaging Assessments																								
Echocardiogram ^m																					X		X	X ^e
Cardiac MRI ^{aa}																					X ^{aa}			
Functional Assessments																								
FVC ^{n,t}																					X		X	X ^e
NSAA ⁿ															X			X	X	X	X	X	X	
Ankle range of motion														X			X	X	X	X	X	X	X	
Ambulatory status													X			X	X	X	X	X	X	X	X	
Actigraphy ^o												X			X	X	X	X						
Clinical Outcome Assessments																								
Caregiver-completed																								
Modified PODCI – Pediatric Parent ^p																		X	X	X	X	X	X	
EQ-5D-Y Proxy ^p																				X		X	X	
EQ-5D-5L																				X		X	X	
PGIS:CG ^p														X			X	X	X	X	X	X	X	
Participant-completed																								
Modified PODCI – Adolescent ^p																					X	X	X	

PFIZER CONFIDENTIAL

CT02-GSOP Clinical Protocol Template Phase 1 2 3 4 (04 September 2018)

Page 204

Period	Year 2																				Long-term follow up		Early Discontinuation Visit ^e	
	Visit 20 ^{a,bb,cc}	Visit 21 ^{bb,cc}	Visit 22 ^{bb,cc}	Visit 23 ^{bb,cc}	Visit 24 ^{bb,cc}	Visit 25 ^{bb,cc} & 26 ^{bb,cc}	Visit 27 ^{bb,cc}	Visit 28 ^{bb,cc}	Visit 29 ^{bb,cc}	Visit 29.2 ^{b,bb,cc}	Visit 30 ^{bb,cc}	Visit 30.1 ^{bb,cc}	Visit 30.2 ^{b,bb,cc}	Visit 31 ^{c,cc}	Visit 31.2 ^{b,cc}	Visit 32 ^{b,cc}	Visit 33	Visit 34	Visit 35	Visits 36, 38, 40, 42 ^d	Visits 37, 39, 41, 43 ^d			
Visit Number/Description	Year 2, Week 1, Day 1	Year 2, Week 1, Day 2	Year 2, Week 1, Day 4	Year 2, Week 1, Day 6	Year 2, Week 1, Day 7	Year 2, Week 2, Days 8 & 9	Year 2, Week 2, Day 10	Year 2, Week 2, Day 14	Year 2, Week 3	Year 2, Week 4	Year 2, Week 5	Year 2, Week 6	Year 2, Week 7	Year 2, Week 9	Year 2, Week 11	Year 2, Week 13	Year 2, Week 18	Year 2, Week 35	Year 2, Week 52	Years 3, 4, 5, 6 ^d	Years 3, 4, 5, 6 ^d	Early Discontinuation Visit ^e		
Visit Day	390	391	393	395	396	397& 398	399	403	410	417	423	431	437	449	463	479	509	629	749	930, 1290, 1650, 2010 ^d	1110, 1470, 1830, 2190 ^d			
Visit Window (\pm days)	3 ^f	2 ^f	2 ^f	2 ^f	2 ^f	2 ^f	2 ^f	3 ^f	3 ^f	3 ^f	3 ^f	3 ^f	3 ^f	3 ^{f,c}	3 ^f	3 ^f	7 ^f	7 ^f	7 ^f	30 ^f	30 ^f			
EQ-5D-Y ^p																							X	X X
PGIS ^p																							X	X X
Clinical evaluator-completed																								
CGIS ⁿ																							X	X X X
Health economic questionnaires																								
HRU:CG																							X	X X
WPAI:DMD Caregiver																							X	X X
Study Interventions																								
Protocol-mandated glucocorticoid regimen ^q	X	X	\rightarrow	\rightarrow	\rightarrow	\rightarrow	\rightarrow	\rightarrow	\rightarrow	\rightarrow	\rightarrow	\rightarrow	\rightarrow	\rightarrow	\rightarrow	\rightarrow	\rightarrow	\rightarrow	\rightarrow	X				
Background glucocorticoid regimen																				X	\rightarrow	\rightarrow	X ^v	X ^v
IP administration	X																							
Ongoing monitoring																								
Concomitant medications	\rightarrow	\rightarrow	\rightarrow	\rightarrow	\rightarrow	\rightarrow	\rightarrow	\rightarrow	\rightarrow	\rightarrow	\rightarrow	\rightarrow	\rightarrow	\rightarrow	\rightarrow	\rightarrow	\rightarrow	\rightarrow	\rightarrow	\rightarrow	\rightarrow	X		
Serious and nonserious adverse event monitoring	\rightarrow	\rightarrow	\rightarrow	\rightarrow	\rightarrow	\rightarrow	\rightarrow	\rightarrow	\rightarrow	\rightarrow	\rightarrow	\rightarrow	\rightarrow	\rightarrow	\rightarrow	\rightarrow	\rightarrow	\rightarrow	\rightarrow	\rightarrow	\rightarrow	\rightarrow	X	

Abbreviations/Acronyms: \rightarrow =continuous monitoring/event; AAV9= adeno associated virus serotype 9; ADA=anti-drug antibody; BP=Blood pressure; CG=Caregiver; CGIS=Clinician Global Impression of Severity; CBCL=Child Behavior Check List; ECG = electrocardiogram; ELISpot= Enzyme-Linked ImmunoSpot; EQ-5D-Y= EuroQol 5

Period	Year 2																						Long-term follow up		Early Discontinuation Visit ^e		
	Visit 20 ^{a,bb,cc}	Visit 21 ^{bb,cc}	Visit 22 ^{bb,cc}	Visit 23 ^{bb,cc}	Visit 24 ^{bb,cc}	Visit 25 ^{bb,cc & 26^{bb,cc}}	Visit 27 ^{bb,cc}	Visit 28 ^{bb,cc}	Visit 29 ^{bb,cc}	Visit 29.2 ^{b,bb,cc}	Visit 30 ^{bb,cc}	Visit 30.1 ^{bb,cc}	Visit 30.2 ^{b,bb,cc}	Visit 31 ^{c,cc}	Visit 31.2 ^{b,cc}	Visit 32 ^{b,cc}	Visit 33	Visit 34	Visit 35	Visits 36,	Visits 37, 39,						
Visit Number/Description	Year 2, Week 1, Day 1	Year 2, Week 1, Day 2	Year 2, Week 1, Day 4	Year 2, Week 1, Day 6	Year 2, Week 1, Day 7	Year 2, Week 2, Days 8 &9	Year 2, Week 2, Day 10	Year 2, Week 2, Day 14	Year 2, Week 3	Year 2, Week 4	Year 2, Week 5	Year 2, Week 6	Year 2, Week 7	Year 2, Week 9	Year 2, Week 11	Year 2, Week 13	Year 2, Week 18	Year 2, Week 35	Year 2, Week 52	Years 3, 4, 5, 6 ^d	Years 3, 4, 5, 6 ^d						
Visit Day	390	391	393	395	396	397& 398	399	403	410	417	423	431	437	449	463	479	509	629	749	930,	1110,	1290,	1470,	1650,	1830,	2010 ^d	2190 ^d
Visit Window (± days)	3 ^f	2 ^f	2 ^f	2 ^f	2 ^f	2 ^f	2 ^f	3 ^f	3 ^f	3 ^f	3 ^f	3 ^f	3 ^f	3 ^f	3 ^f	3 ^f	7 ^f	7 ^f	7 ^f	30 ^f	30 ^f						

Dimensions—Youth; FVC= Forced Vital Capacity; IP=investigational product; NAb=neutralizing antibodies; NSAA=North Star Ambulatory Assessment; PGIS= patient global impression of severity; PODCI=Pediatric Outcomes Data Collection Instrument; PR=pulse rate; temp=temperature.

a. Visit 20 – Year 2, Week 1, Day 1

- Prior to IP administration, the Investigator must confirm applicable Year 2 IP administration eligibility criteria ([Section 7.1](#));
- Participants are to be admitted to the site;
- Participants will be instructed not to take their background glucocorticoid dose on Day 390 (Visit 20);
- The following assessments must be performed prior to IP administration: Physical examination, blood collection (ELISpot to mini-dystrophin and AAV9), urine sample collection, ECG and vital signs;
- Participants will receive an intravenous infusion of 2 mg/kg of methylprednisolone approximately 1 to 4 hours prior to infusion of IP;
- IP administration over approximately 2 to 4 hours (-15 minutes or +30 minutes including flush);
- Vital signs will be monitored at approximately 30 minutes, 1, 2, 4, 8, and 10 hours after start of infusion, and 3 times per day after that for the duration of the hospital stay. Participants will remain as inpatients for at least 7 days after the infusion has terminated and will be discharged on Day 397, or later if deemed necessary by the Investigator (see [Section 8.2.10](#)).
- If adverse events (AEs) possibly related to IP administration are observed, participants should not be discharged until the events have resolved. Upon discharge, participants should stay near the site for at least 7 additional days to enable prompt follow-up in the event of any emergent AEs through Day 403 (Visit 28), or longer if deemed necessary.
- If the time between the blood draw for the clinical safety laboratory tests on Day 360 Visit (Visit 19) and the planned Day 390 Visit (Visit 20) exceeds 13 weeks (90 days), due to operational or administrative reasons (eg, enrollment pause due to regulatory or safety review, operational issues causing significant delays), then the clinical safety laboratory tests should be repeated and eligibility (re)confirmed prior to administering IP. The participant will not be withdrawn due to exceeding the time between Day 360 Visit (Visit 19) and Day 390 Visit (Visit 20), as described in [Section 7.1](#).

PFIZER CONFIDENTIAL

CT02-GSOP Clinical Protocol Template Phase 1 2 3 4 (04 September 2018)

Period	Year 2																				Long-term follow up		Early Discontinuation Visit ^e
	Visit 20 ^{a,bb,cc}	Visit 21 ^{bb,cc}	Visit 22 ^{bb,cc}	Visit 23 ^{bb,cc}	Visit 24 ^{bb,cc}	Visit 25 ^{bb,cc} & 26 ^{bb,cc}	Visit 27 ^{bb,cc}	Visit 28 ^{bb,cc}	Visit 29 ^{bb,cc}	Visit 29.2 ^{bb,cc}	Visit 30 ^{bb,cc}	Visit 30.1 ^{bb,cc}	Visit 30.2 ^{bb,cc}	Visit 31 ^{cc}	Visit 31.2 ^{bb,cc}	Visit 32 ^{bb,cc}	Visit 33	Visit 34	Visit 35	Visits 36, 38, 40, 42 ^d	Visits 37, 39, 41, 43 ^d		
Visit Number/Description	Year 2, Week 1, Day 1	Year 2, Week 1, Day 2	Year 2, Week 1, Day 4	Year 2, Week 1, Day 6	Year 2, Week 1, Day 7	Year 2, Days 8 & 9	Year 2, Week 2, Day 10	Year 2, Week 2, Day 14	Year 2, Week 3	Year 2, Week 4	Year 2, Week 5	Year 2, Week 6	Year 2, Week 7	Year 2, Week 9	Year 2, Week 11	Year 2, Week 13	Year 2, Week 18	Year 2, Week 35	Year 2, Week 52	Years 3, 4, 5, 6 ^d	Years 3, 4, 5, 6 ^d	Early Discontinuation Visit ^e	
Visit Day	390	391	393	395	396	397& 398	399	403	410	417	423	431	437	449	463	479	509	629	749	930, 1290, 1650, 2010 ^d	1110, 1470, 1830, 2190 ^d		
Visit Window (\pm days)	3 ^f	2 ^f	2 ^f	2 ^f	2 ^f	2 ^f	2 ^f	3 ^f	3 ^f	3 ^f	3 ^f	3 ^f	3 ^f	3 ^f	3 ^f	3 ^f	7 ^f	7 ^f	7 ^f	30 ^f	30 ^f		

- If, due to operational or administrative reasons (eg, enrollment pause due to regulatory or safety review, operational issues causing significant delays), a participant's Year 2 IP administration must be delayed, the Day 390 (Visit 20) and also subsequent visits will be delayed for that participant until the pause is lifted. If the pause is not lifted within 6 months of the Day 360 (Visit 19), the participant will undergo an unplanned visit for general monitoring on Day 540 ± 7 days, and approximately every 6 months afterwards until the pause is lifted (or more frequently if considered necessary by the investigator) for sites in Israel, see [Appendix 16](#).

b. Visits 29, 29.2, 30.2, 31.2, and 32

- Unless clinical concern and/or participant preference and/or the site's institutional review board's preference warrants in-person visit, this visit may be performed remotely, and would include blood collection at or close to the participant's home coordinated by local phlebotomist, as well as phone communication between site staff and participant/caregiver to discuss any adverse events and/or changes to concomitant medications.

c. Visit 31 must be conducted in the course of two (preferably consecutive) days in order to comply with daily blood volume limits. Unless clinical concern and/or participant preference and/or the site's institutional review board's preference warrants in-person visit, the follow-up day visit, on the second day, to complete blood collection, may be performed remotely, to allow blood collection at or close to the participant's home. The following laboratory assessments must be collected as follows:

- Visit 31 (Year 2, Week 9)
 - First day: ELISpot to mini-dystrophin and AAV9, viral vector shedding.
 - Second day: clinical safety, cardiac troponin I, biomarker (creatinine kinase).

d. Visit 42 and 43 – Long-term follow up Year 6

- All participants will be followed for 5 years after receiving fordadistrogene movaparvovec. Therefore Visits 42 and 43 only apply to participants randomized to Cohort 2.

e. Early Discontinuation Visit

- This visit is not applicable for Cohort 2 participants who were withdrawn from the study between Day 360 (Visit 19) and Day 390 (Visit 20) (see [Section 7](#)).
